8. STATISTICAL CONSIDERATIONS

8.1 DETERMINATION OF SAMPLE SIZE

The recurrence rate of head and neck cancer is 80% over 2 years (50 to 60% local recurrence and 20 to 30% distant recurrence [41]. In the Phase I trial of PepCan described above the overall histological regression rate of HSILs was 45% [36]. A reduced recurrence rate by the magnitude of 45% would reach 44%. Vaccinating 72 subjects in the PepCan arm and 24 subjects in the placebo arm would have 90% power at alpha of 5%, 2 tailed. Accounting for about 5% drop out rate, 75 subjects would be needed in the PepCan arm, and 25 subjects in the placebo arm.

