5. STUDY POPULATION

5.1 INCLUSION CRITERIA

In order to be eligible to participate in this study, an individual must meet all of the following criteria:

- 1. Able to provide informed consent
- 2. Male or female 18 years of age or older
- 3. Squamous cell carcinoma of the head and neck who have completed curative therapy (surgery and/or radiation and/or chemotherapy) within the previous 120 days
- 4. Performance status of ECOG 0-2
- 5. No Evidence of Disease (NED) based on clinical and/or radiographic evaluations
- 6. Vital Signs recorded
 - a. Blood pressure (BP) (<200/120mm Hg)
 - b. Heart rate (50-120 beats per min)
 - c. Respiratory rate (<25 breaths per min)
 - d. Temperature (<100.4°F)
- 7. Blood work done at Screening Visit
 - a. White count ($\geq 3x10^9/L$)
 - b. Hemoglobin ($\geq 7 \text{ g/dL}$)
- 8. Willing and able to comply with the requirements of the protocol

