5.2 EXCLUSION CRITERIA

An individual who meets any of the following criteria will be excluded from participation in this study:

- 1. Positive urine pregnancy test for women of childbearing potential
- 2. Being pregnant or attempting to be pregnant with the period of study participation
- 3. Women who are breast feeding or plan to breast feed within the period of study participation
- 4. Patients who are allergic to Candin® or yeast
- 5. History of severe asthma requiring emergency room visit or hospitalization within the past 5 years
- 6. Patients who have previously received PepCan
- 7. History of recurrence of squamous cell carcinoma of the head and neck
- 8. If in the opinion of the PIs or other Investigators, it is not in the best interest of the patient to enter or continue in this study

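### Section 8.1 does not assure 90% power: the planned Fisher's exact test gives 87% even at 80% vs 44%, and the 80% control rate holds at its range midpoints only if local and distant recurrence never overlap

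*Combined protocol and SAP*

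**What the plan says.** Section 8.1 gives the control rate and its only explanation in one sentence, with a single citation: "The recurrence rate of head and neck cancer is 80% over 2 years (50 to 60% local recurrence and 20 to 30% distant recurrence". No other any-recurrence figure for head and neck cancer appears in the document.

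The effect size comes from the Phase I trial in cervical lesions, where "the overall histological regression rate of HSILs was 45" percent. Applied as a relative reduction, this gives the PepCan-arm rate: "A reduced recurrence rate by the magnitude of 45% would reach 44" percent. The power statement follows: "Vaccinating 72 subjects in the PepCan arm and 24 subjects in the placebo arm would have 90% power at alpha of 5%, 2 tailed". An allowance of about 5% for dropout brings the totals to 75 and 25.

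Section 7.3 names Fisher's exact test for the two-year comparison of recurrence between arms. Under section 5.5, a subject judged to be in recurrence joins the recurrence group and completes participation, so each subject can contribute only one recurrence.

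On the population, section 5.1 requires "No Evidence of Disease (NED) based on clinical and/or radiographic evaluations" and completion of curative therapy within the previous 120 days. Section 5.2 excludes subjects with a "History of recurrence of squamous cell carcinoma of the head and neck". Visit 1 may fall up to 90 days after screening (section 7.1), and the synopsis starts the two-year follow-up at the first injection.

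**The concern.** The trial counts subjects with any recurrence. A local rate and a distant rate add up to that proportion only if no patient appears in both. Section 8.1 offers two component ranges in support of a single total, the midpoints add exactly to that total, and nothing is said about overlap. The reader cannot tell whether 80% is a first-event rate or a sum that counts some patients twice.

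The starting point of the 80% is also missing. Trial follow-up begins after a disease-free assessment, and up to about 210 days after therapy (120 + 90, if the 120 days are counted to screening). The plan does not say whether recurrences before that point are included in the 80%.

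Separately, the 90% does not match the test the plan intends to use.

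Recurrence is a secondary endpoint, with safety primary, but it is the only basis given for the sample size, and section 4.1 says the trial is designed to show efficacy on it. There are 24 evaluable placebo subjects. If the control rate is lower than assumed, the same 45% relative reduction is a smaller absolute difference, and a null result could be given more weight than it deserves because of the 90% claim.

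**Working it through.** **Inputs.** From section 8.1: control rate 80%; local 50–60%; distant 20–30%; relative reduction 45%; 72 PepCan and 24 placebo evaluable; alpha 5%, two-sided. From section 7.3: Fisher's exact test.

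**1. Reproduce the plan's figure.** PepCan rate: 0.80 × (1 − 0.45) = 0.44. The pooled, uncorrected normal approximation to the chi-square test is

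power = Φ[(p₁ − p₂ − 1.96·SE₀) / SE₁]

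- Pooled rate: (24 × 0.80 + 72 × 0.44) / 96 = 0.53.
- SE₀ = √[0.53 × 0.47 × (1/24 + 1/72)] = 0.1176.
- SE₁ = √[0.80 × 0.20/24 + 0.44 × 0.56/72] = 0.1004.
- Power = Φ[(0.36 − 1.96 × 0.1176) / 0.1004] = Φ(1.29) = 90.1%.

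The matching sample-size formula returns 24 + 72. The plan's arithmetic is right for this formula.

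**2. Use the planned test.** Summing the binomial probabilities of all outcomes with a two-sided Fisher p-value of 0.05 or less, at 80% vs 44%, gives 87.0% at 72/24. With all 75/25 enrolled subjects and no dropout it gives 89.0%. Both are below 90%.

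**3. What the components imply.** Any-recurrence rate = local + distant − both.

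- No overlap: 50 + 20 = 70% up to 60 + 30 = 90%; midpoints 55 + 25 = 80%.
- Independent (assumption): 1 − 0.50 × 0.80 = 60% up to 1 − 0.40 × 0.70 = 72%; midpoints 1 − 0.45 × 0.75 = 66.25%.
- Every distant case also local (assumption, extreme bound): 50% to 60%; midpoint 55%.

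For the total to be 80%, the overlap must equal local + distant − 80. This is 0 at the midpoints and at most 60 + 30 − 80 = 10 points at the upper ends.

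**4. Power at 72/24 with the 45% relative reduction kept.**

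| Control rate | PepCan rate | Basis | Fisher | Pooled chi-square |
|---|---|---|---|---|
| 80% | 44% | as stated; no overlap at midpoints | 87.0% | 90.1% |
| 72% | 39.6% | independent, upper ends | 75% | 80% |
| 66.25% | 36.4% | independent, midpoints | 66% | 73% |
| 60% | 33% | independent, lower ends; or nested, upper end | 57% | 65% |
| 55% | 30.25% | nested, midpoint | 51% | 59% |
| 50% | 27.5% | nested, lower end | 46% | 53% |

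The change of test accounts for the gap between the last two columns. The change of control rate accounts for the fall down each column. Like for like, independence at the midpoints costs 17 points by the pooled formula (90% to 73%) and 21 points by Fisher (87% to 66%).

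**The case against.** The strongest reply is that no error in the 80% has been shown. Section 8.1 never says the rates were added; that is inferred from the parenthesis and the midpoint match. If the cited source classifies each patient once, by site of first failure, adding is correct. The trial's own endpoint works that way, since section 5.5 ends participation at recurrence. Within the stated ranges, 80% can also accommodate up to 10 points of overlap. The independence and nesting figures are assumptions, and nesting is an extreme bound. All of this stands. A reader might infer that 80% can be reached only by double counting, but the documents do not support that.

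A reader might also infer that a disease-free population with no prior recurrence must have a rate well below 80%. The documents do not support this either. A recurrence rate already presupposes remission, and no rate for such subjects, counted from first injection, is given anywhere. The delay to first injection leaves the starting point undefined, but it fixes neither the direction nor the size of any difference.

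Finally, safety is the primary endpoint of this Phase I/II trial, which limits the consequence.

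The reply leaves two things unanswered. The plan does not say that the categories are exclusive, and the 90% is not the power of the planned test even if 80% is accepted in full.

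**Conclusion.** The point holds as a statement that 90% power is not assured. It does not show that the calculation was done wrongly or that the true control rate is lower than 80%.

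One part needs no assumption beyond the plan's own inputs: Fisher's exact test at 72/24 and 80% vs 44% has 87.0% power, 3 points under the stated figure.

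The other part is conditional. At the midpoints of the plan's ranges, 80% requires that no patient has both local and distant recurrence. If they do overlap, Fisher power at the midpoints is about 66% under independence and about 51% under full nesting. These figures assume that the 45% relative reduction still applies at the lower control rate and that 72 and 24 subjects are evaluable.

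**What to change.** In section 8.1:

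- Replace the single 90% claim with Fisher power of about 87% at an 80% control rate and 72/24 evaluable subjects.
- State whether 80% is an any-recurrence (first-event) rate with each patient counted once, and the time point from which the two years run in the cited source.
- Add a sensitivity table of Fisher power at control rates of 80%, 66% (66.25% before rounding) and 55%: about 87%, 66% and 51%. Label the last two as overlap assumptions (independent, and fully nested as the extreme bound).

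The sample size stays at 100, and enrolment, treatment and visits do not change. The cost is a few sentences and a small table; the downside is a less favourable stated power.

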PepCan was first tested in human to treat biopsy-proven high-grade squamous intraepithelial lesions (HSILs) in a Phase I single-arm, single-site study (NCT01653249). Subjects (n=52) were enrolled between September 2012 and January 2015, and those with biopsy-proven cervical intraepithelial neoplasia (CIN) 2/3 (n=34) (synonymous to HSIL) were eligible for vaccination. The initial part of the clinical trial was doseescalation in style in which six subjects each were consecutively assigned to increasing amounts of HPV-16 E6 peptides (50 μg/peptide, 100 μg/peptide, 250 μg/peptide, and 500 μg/peptide). The amount of Candin® was constant at 300 µL. After the dose escalation phase, an additional 10 subjects were vaccinated at the optimal dose of 50 µg/peptide as determined by histological regression. At the screening visit, the cervix was visualized under a colposcope after applying acetic acid, biopsies were obtained, Thin-Prep (Hologic, Marlborough, MA) was collected for HPV-DNA testing (Linear Array HPV Genotyping Test, Roche Molecular Diagnostics, Pleasanton, CA), and routine laboratory testing was performed (complete blood count, sodium, potassium, chloride, carbon dioxide, blood urea nitrogen, creatinine, aspartate transaminase, alanine transaminase, lactate dehydrogenase, γ-glutamyl transpeptidase, total bilirubin, and direct bilirubin). Subjects who already were diagnosed with biopsy-proven CIN2/3 were also eligible as long as the first vaccine injection could be given within 60 days, and other inclusion criteria were met (ages 18 to 50 years old, blood pressure ≤ 200/120 mm Hg, heart rate 50 to 120 beats per minute, respiration \leq 25 breaths per minute, temperature \leq 100.4°F, white count \geq 3 x 109/L, hemoglobin \geq 8 g/dL, and platelet count ≥ 50 x 109/L). Being positive for HPV-16 was not required due to possible crossprotection [19, 20, 22, 23] and de novo immune stimulation [24, 25]. Exclusion criteria included a history of disease or treatment causing immunosuppression, pregnancy, breast-feeding, allergy to Candida, a history of severe asthma, current use of beta-blocker, and a history of invasive squamous cell carcinoma of the cervix. Urine pregnancy test was performed prior to each injection, and blood was drawn for routine laboratory testing and immunological assessments immediately prior to the first and third injections. The vaccine was administered intradermally in any limb. Twelve weeks after the last injection, blood was drawn, ThinPrep sample was collected and LEEP was performed. The study gynecologists described the presence of visible lesions and their locations. Digital photographs were taken as additional documentation. Pre-vaccination biopsies from the screening visits and post-vaccination LEEP biopsies were read by the staff pathologists at the study institution. In addition, the study pathologist reviewed all slides of all LEEP samples. The highest grade of pathology found in any lesion was used to determine eligibility to be vaccinated and to assess histological response. Safety and tolerability were assessed from the time informed consent was obtained until the day LEEP was performed using the National Cancer Institute Common Terminology Criteria for Adverse Events (NCI CTCAE) Version 4.0. Dose-limiting toxicities were defined as vaccine-related allergic and autoimmune AEs greater than grade 1 and any other AEs greater than grade 2. Efficacy was based on histological grading of the LEEP samples. A subject with no dysplasia or cervical intraepithelial neoplasia 1 (CIN 1) was considered to be a complete responder, and a subject with CIN2/3 measuring ≤ 0.2 mm2 was considered to be a partial responder (ScanScope® CS and ImageScope™ software, Aperio, Vista, CA). When responders and non-responders were compared, complete and partial responders were combined.

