
One hundred thirty-two injections have been given to 34 subjects. No dose limiting toxicities were reported. The most common AEs were immediate and delayed injection-site reactions. Although delayed injection-site reaction was defined as occurring at or more than 24 hours after injection, it was not uncommon for it to appear a few to several days after injection. More grade 2 immediate injection-site reactions but not delayed injection-site reactions were recorded at the higher two doses compared to the lower two doses (odds ratio of 6.3 [1.98, 20.3], p<0.0001, for the immediate reaction; and 2.0 [0.6, 7.1], p=0.3, for the delayed reaction). Other vaccine-related or possibly vaccine-related AEs, which occurred with \geq 5% of injections, in the order of decreasing number of occurrences, were myalgia, headache, nausea, fatigue, hypokalemia, fever, and flu-like symptoms. None of these AEs was greater than grade 2.

The histological response rates in order of increasing doses were 50%, 50%, 33%, and 40%. The overall histological response rate was 45%, and none progressed to cervical squamous cell carcinoma. In comparison, a historical placebo group in another clinical trial of HPV therapeutic vaccine with a similar study reported a regression rate of 22% [26]. No statistically significant differences were detected when histological response rates were compared (1) between subjects with entry diagnosis of CIN 2 versus CIN3, (2) between subjects \leq 25 years of age versus > 25 years of age, and (3) between subjects who were HPV-16-positive versus those who were not. The mean number of cervical quadrants with visible lesions decreased significantly from 1.9 quadrants to 0.8 quadrants after vaccination (p=0.001).

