7.3 EFFICACY ASSESSMENTS

Studying the efficacy of PepCan and the schedule in which this protocol specifically outlines the clinical response (i.e., reduced cancer recurrence rate) of subjects is a secondary endpoint. Immune response will be evaluated as the tertiary endpoint, and microbial response will be assessed as the quaternary endpoint. This section includes a list and description of the procedures that will be conducted.

ASSESSMENT OF CLINICAL EFFICACY

Cancer recurrence rate will be compared for a 2-year period between the PepCan and placebo arms using Fisher's exact test.

COLLECTION OF BIOLOGICAL SPECIMEN AND URINE SPECIMEN

URINE SPECIMEN

A urine pregnancy test will be administered to subjects of childbearing potential at every visit and the results reviewed by the study team before injection.

ORAL WASH SPECIMEN

- 1. Oral wash specimens will be collected at Screening, Visit 5, Visit 7 and Visit 8.
- 2. Subjects will be asked to swish 10mL of mouthwash and spit into a cup.

BLOOD DRAW

- 1. Blood draw will be performed by a trained phlebotomist or other medical professional
- 2. CBC with differential on Visits Screen, 1, 3, 5, 6, 7, 8, 9
- 3. Chem 7 on Visits Screen, 1, 3, 5, 6, 7, 8, 9
- 4. LFTs on Visits Screen, 1, 3, 5, 6, 7, 8, 9
- 5. 8 rubber green top tubes on Visits 1, 5, 8, 9

STOOL SAMPLE

- 1. Stool samples will be collected with OMNIgene•GUT kit (ref. OMR-200) which includes a toilet accessory sheet, collection tube, and spatula.
- 2. Subjects will be given appropriate packing and shipping supplies to be sent back to UAMS at Visits Screen, 5, 7, and 8 to the following address:

Cancer Clinical Trials Office

[name]

[name]

3. Instructions will be given to the subject at each visit, but the full instructions for the kit can also be found at: http://www.dnagenotek.com/US/support/ciOMR200.html

FUTURE USE OF REMAINING SAMPLES

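### Section 8.1 uses the uncontrolled 45% HSIL regression rate in full as the effect versus placebo and ignores the 22% placebo regression rate in section 2.1, so the stated 90% power is not supported

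*Combined protocol and SAP*

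**What the plan says.** Section 8.1 starts from a control rate: "The recurrence rate of head and neck cancer is 80% over 2 years". It then takes the overall HSIL regression rate of 45% from the Phase I trial and applies it as a proportional reduction: "A reduced recurrence rate by the magnitude of 45% would reach 44" percent. From these two rates it concludes: "Vaccinating 72 subjects in the PepCan arm and 24 subjects in the placebo arm would have 90% power", with a two-tailed alpha of 5%. About 5% dropout brings the total to 75 plus 25.

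Section 2.1 describes the source of the 45%. PepCan was tested "in a Phase I single-arm, single-site study", so that rate has no concurrent comparator. The same section then supplies an external one: "a historical placebo group in another clinical trial of HPV therapeutic vaccine with a similar study reported a regression rate of 22" percent. It also gives the results by dose: "The histological response rates in order of increasing doses were 50%, 50%, 33%, and 40" percent. The lowest dose, 50 µg per peptide, is the one used in the present trial.

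Section 7.3 names the efficacy analysis: "Cancer recurrence rate will be compared for a 2-year period between the PepCan and placebo arms using Fisher's exact test".

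**The concern.** A randomised comparison with placebo can show only what PepCan adds to placebo. A single-arm regression rate includes lesions that would have regressed anyway, and the protocol's own background puts a figure on that share. Section 8.1 nevertheless carries the gross 45% straight into the between-arm difference.

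Recurrence is a secondary endpoint, but it is the only one used to size the trial. If the true net effect is smaller than 45%, a null recurrence result would be much less informative than the stated 90% power suggests, and 8.1 gives no hint of this.

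**Working it through.** **Inputs.** From section 8.1: control recurrence 80%, effect 45%, 72 PepCan and 24 placebo subjects, two-sided 5%. From section 2.1: overall response 45%, response at the 50 µg dose 50%, historical placebo regression 22%. From section 7.3: Fisher's exact test.

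**Step 1: reproduce the plan's figure.** The PepCan rate is 0.80 × (1 − 0.45) = 0.44. In the pooled-variance normal formula:

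- pooled rate = (24 × 0.80 + 72 × 0.44)/96 = 0.53
- standard error under the null = √[0.53 × 0.47 × (1/24 + 1/72)] = 0.1176
- standard error under the alternative = √[0.80 × 0.20/24 + 0.44 × 0.56/72] = 0.1004
- z = (0.36 − 1.96 × 0.1176)/0.1004 = 1.29, so power = 90.1%

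This matches the stated 90%. Section 8.1 therefore used 45% as the full relative reduction versus placebo. Reading 45% as percentage points (80% to 35%) would give 98.7%, which does not match.

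**Step 2: use the planned test.** Summing binomial probabilities over all outcomes with a two-sided Fisher p ≤ 0.05 gives 87.0% for the same rates and group sizes.

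**Step 3: allow for the 22%.** The documents define no rule for this, so three simple ones are shown, each starting from the overall 45% and from the 50% at the 50 µg dose. Placebo recurrence stays at 80%.

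| Rule | PepCan recurrence | Fisher power | Pooled formula |
|---|---|---|---|
| As planned, no allowance | 0.80 × 0.55 = 44.0% | 87% | 90% |
| Ratio of non-regression rates, from 45% | 0.80 × 0.55/0.78 = 56.4% | 52% | 55% |
| Difference in points, from 45% | 80 − 23 = 57.0% | 50% | 53% |
| Difference used as a relative reduction, from 45% | 0.80 × 0.77 = 61.6% | 35% | 36% |
| Ratio, from 50% | 0.80 × 0.50/0.78 = 51.3% | 69% | 72% |
| Difference in points, from 50% | 80 − 28 = 52.0% | 67% | 70% |
| Difference as a relative reduction, from 50% | 0.80 × 0.72 = 57.6% | 49% | 50% |

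**Step 4: what the design needs, whatever the rule.** With 80% in the control arm and 72/24 subjects, Fisher power of 80% requires a net relative reduction of about 41% (PepCan recurrence 47.3%). Fisher power of 90% requires about 47% (42.2%).

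**Step 5: the control rate.** Section 8.1 gives components: "The recurrence rate of head and neck cancer is 80% over 2 years (50 to 60% local recurrence and 20 to 30% distant recurrence". Their sums run from 50 + 20 = 70% to 60 + 30 = 90%, if local and distant recurrence are taken not to overlap, as the 80% itself seems to assume. Keeping the 45% reduction, Fisher power is 72% at a control rate of 70% (0.70 × 0.55 = 38.5%), 87% at 80%, and 97% at 90% (0.90 × 0.55 = 49.5%).

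**The case against.** The strongest reply is that 8.1 contains no calculation error and states its rates openly, and that every power figure is conditional on the rates assumed. The netted figures, on this view, correct nothing. HSIL regression and head and neck cancer recurrence are different endpoints, the 22% comes from another trial, and section 2.1 does not say whether regression was defined alike in the two. In particular, it does not say whether the 45% includes the partial responders described there. The 45% also followed four injections, while this trial gives seven. A spread from 35% to 69% shows that the documents cannot fix the size of the loss. Finally, recurrence is secondary to safety in a Phase I/II trial.

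Much of this stands as a limit on the numbers: no single netted power is the right one. It does not rescue the input. Section 8.1 already makes the transfer from regression to recurrence, without comment. If the 45% can be carried across, its comparator has to be addressed; if it cannot, the 44% has no stated basis. The direction does not depend on the three rules either. Carrying over the odds ratio, or the ratio of response rates, gives Fisher power of about 44% to 64%. A longer regimen might do better, but 8.1 does not argue that.

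**Conclusion.** The concern holds. The arithmetic in 8.1 is right and the effect size is unsupported: an uncontrolled rate is used as a placebo-controlled effect, although section 2.1 cites a comparator that undercuts it. Even if the net reduction really is 45%, the planned Fisher test has 87% power, not 90%. With allowance for the 22%, Fisher power is about 35% to 69%.

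That range assumes an 80% control rate, 72 and 24 evaluable subjects, comparable definitions of regression in the two sources, and transfer of the effect from HSIL to cancer recurrence. The omission is certain; the size of the shortfall is illustrative.

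**What to change.** Leave the 100 subjects and Fisher's exact test unchanged, and amend section 8.1 as follows:

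1. State that power of about 90% (87% under the planned Fisher test) requires PepCan to cut recurrence by 45% net of placebo. Justify that figure or call it an assumption.
2. Cite the 22% placebo regression rate from section 2.1.
3. Add a short sensitivity table naming the netting rule and the test. It should show Fisher power of about 35% to 69% for placebo-adjusted effects, and 72%, 87% and 97% for control rates of 70%, 80% and 90% with a 45% reduction.
4. Say that any netted effect is itself an assumption: the 22% is from another trial, the responder definitions may differ, the 45% followed four injections rather than seven, and both rates concern HSIL regression.

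In the efficacy analysis, report the difference in recurrence with a 95% confidence interval beside the Fisher p-value, so that a null result can be read against the effects it does and does not exclude.

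The cost is one paragraph, one small table and a less favourable power statement. Enrolment and procedures do not change.

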4. STUDY DESIGN

4.1 OVERALL DESIGN

This is a Phase I/II randomized, double-blind, placebo controlled, multi-site study of PepCan. It is designed to show the safety and efficacy of a 7-dose regimen of PepCan over a two-year period in terms of reducing cancer recurrence rate by comparing the recurrence rates between the PepCan and the placebo arm. The ratio of the number of subjects who will receive PepCan versus placebo will be 3:1. The study randomization schematic will be constructed by the Study Statistician. Subjects will be randomized in a 3:1 ratio to PepCan or placebo, and randomization will be done in a book form by Research Pharmacy. Up to 150 subjects will be for screened until 100 subjects are eligible for injection.

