8.2 STATISTICAL ANALYSES

Subjects who received at least one dose of the vaccine will be included in safety assessments. Safety analyses will include summaries of the incidence of AEs using the NCI CTCAE Version 5.0 that occur during the study period regardless of causality. The AEs will be mostly descriptive initially. However, after unblinding at the completion of the study, rates of common side effects (occurring with 5% or more injections) will be compared between the PepCan and the placebo arms. Efficacy will be assessed by comparing cancer recurrence rate between the 2 arms. The expected number of head and neck cancer patients who achieve remission is 100 patients per year. For immunological assessments, the presence of new anti-HPV-16 E6 T-cell activity will be measured using CD3 ELISPOT assay, and its statistical significance will be assessed using a paired *t*-test. For analyses of immune cells such as Th1, Th2, Treg, and MDSCs, percentages before and after vaccination will also be assed using a two-tailed paired *t*-test. The frequencies between subjects who experience recurrence and those that do not in the PepCan arm will be compared using Wilcoxon rank-sum test. The diversity of gut microbiome will be assessed prior to

injection, and will be compared to that after injection using alpha diversity, beta diversity, and compositions at the phylum or family levels. These parameters will also be compared between subjects with and without recurrence with in the PepCan arm.

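### The 90% power in section 8.1 is not that of the planned Fisher's exact test, which has about 87% with 72 + 24 subjects

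*Combined protocol and SAP*

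**What the plan says.** Section 8.1 gives the design assumptions. For placebo: "The recurrence rate of head and neck cancer is 80% over 2 years". For PepCan: "A reduced recurrence rate by the magnitude of 45% would reach 44" percent. From these it concludes: "Vaccinating 72 subjects in the PepCan arm and 24 subjects in the placebo arm would have 90% power at alpha of 5%, 2 tailed". Allowing for drop-out of about 5%, it then sets enrolment at 75 and 25. Neither a test nor a sample-size formula is named. The 3:1 split matches section 4.1.

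The test appears in section 7.3, under the assessment of clinical efficacy: "Cancer recurrence rate will be compared for a 2-year period between the PepCan and placebo arms using Fisher's exact test".

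Section 8.2 says of this endpoint only: "Efficacy will be assessed by comparing cancer recurrence rate between the 2 arms". The same section does name tests for the immunological endpoints (paired t-test, Wilcoxon rank-sum).

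**The concern.** A power figure should belong to the test that will be run. Fisher's exact test is conservative at these sample sizes, so a power figure from an uncorrected large-sample formula will usually be too high for it. Section 8.1 does not say which method was used, and a reader who takes the 90% together with section 7.3 will attribute it to Fisher's test.

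Recurrence is the secondary endpoint, but it is the only comparison with a power statement and the sole basis for the 100 subjects. The mismatch affects two things: whether the sample-size statement can be reproduced, and how much reassurance a non-significant result would carry. It does not affect the validity of the test or the estimate.

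**Working it through.** **Inputs (all from the protocol).** Placebo rate p₀ = 0.80 and PepCan rate p₁ = 0.80 × (1 − 0.45) = 0.44 (section 8.1); n₁ = 72, n₀ = 24; two-sided α = 0.05; Fisher's exact test on the 2-year proportions (section 7.3).

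**Step 1: reproduce the stated 90%.** Pooled normal approximation, no continuity correction:

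- Pooled rate: (72 × 0.44 + 24 × 0.80) / 96 = 50.88 / 96 = 0.53.
- Null standard error: √[0.53 × 0.47 × (1/72 + 1/24)] = 0.1176.
- Alternative standard error: √[0.44 × 0.56/72 + 0.80 × 0.20/24] = 0.1004.
- Power = Φ[(0.36 − 1.96 × 0.1176) / 0.1004] = Φ(1.289) = 90.1%.

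Solving the same formula for 90% power at 3:1 gives 24 placebo subjects, hence 72 on PepCan, exactly the protocol's numbers. The arcsine approximation gives Φ(|2 arcsin√0.80 − 2 arcsin√0.44| × √(72 × 24/96) − 1.96) = Φ(0.7638 × 4.243 − 1.96) = 90.0%. Exact enumeration of the uncorrected chi-square test gives 90.1%. The figure is thus right for an uncorrected large-sample test, although the protocol does not say which method was used.

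**Step 2: power of the planned test.** For each of the 25 × 73 possible outcomes (x recurrences among 24, y among 72), compute the two-sided Fisher p-value. Then sum the probabilities Bin(x; 24, 0.80) × Bin(y; 72, 0.44) over the outcomes with p ≤ 0.05.

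| PepCan + placebo evaluable | Fisher power, usual two-sided p | Fisher power, doubled one-sided p |
|---|---|---|
| 72 + 24 | 87.0% | 85.2% |
| 75 + 25 | 89.0% | 87.4% |
| 78 + 26 | 91.2% | 87.8% |

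The usual two-sided p sums the probabilities of all tables no more likely than the one observed. With that definition, 78 + 26 is the smallest 3:1 size that reaches 90%.

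**Step 3: where the loss comes from.** Enumerating under a common rate in both arms gives Fisher's actual size at 72 + 24:

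| Common recurrence rate | 0.44 | 0.50 | 0.60 | 0.70 | 0.80 |
|---|---|---|---|---|---|
| Actual two-sided size | 3.33% | 3.36% | 3.42% | 3.75% | 3.26% |

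The maximum over all common rates is 3.8%, against a nominal 5%.

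**Step 4: the gap on the effect scale.** With placebo at 80%, Fisher's test reaches 90% power at a PepCan rate of 42.2% with 72 + 24, or 43.4% with 75 + 25, instead of the assumed 44%.

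**The case against.** The strongest reply is that neither sentence is false in isolation. Section 8.1 claims 90% without attaching it to Fisher's test, section 7.3 names Fisher's test without claiming any power, and sizing by a normal approximation before analysing with an exact test is common. That explains how the gap could arise. It does not make 90% the power of the planned analysis.

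A second reply is that the gap is small beside the uncertainty in the inputs. Section 8.1 builds the 80% from 50 to 60% local and 20 to 30% distant recurrence, which sum to anything from 70% to 90%. Keeping the 45% relative reduction, Fisher power at 72 + 24 runs from 71.7% (70% vs 38.5%) to 97.3% (90% vs 49.5%). This is fair and should temper how much weight anyone puts on three points. It is a separate matter, though: the shortfall here is present at the protocol's chosen rates.

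Third, with no drop-out the shortfall is only 1 point, and nothing about the design, test or enrolment has to change. Both statements are correct, and they limit the importance of the point. Reading a non-significant result should in any case rest mainly on the estimate and its confidence interval.

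Fourth, 87% itself depends on how the two-sided p-value is defined. That stands, and the corrected sentence should state the definition. The alternative definition makes the power lower, not higher.

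Finally, section 7.3 already prespecifies the test, so repeating it in section 8.2 is only tidying. That also stands.

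**Conclusion.** The concern holds. With 72 + 24 evaluable subjects, 44% vs 80% and a two-sided 5% level, the planned Fisher's exact test has 87.0% power, 3.0 points below the stated 90%. With all 75 + 25 evaluable it has 89.0%, 1.0 point below. Type II error is about 13% (11% with no drop-out) rather than 10%. These figures use the usual two-sided definition; doubling the one-sided p-value gives 85.2% and 87.4%. The 90% is not an arithmetic slip, since it is correct for an uncorrected large-sample test, but that is not the test the protocol names. The consequence is modest: a power statement that is slightly too favourable and cannot be reproduced from the stated analysis, with no bias and no inflation of type I error.

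**What to change.** Replace the power sentence in section 8.1 with, for example: *With 72 and 24 evaluable subjects, a two-sided 5% Fisher's exact test has about 87% power for 44% vs 80%.* Add the two-sided definition used (sum of the probabilities of all tables no more likely than the one observed), so that the figure can be reproduced. It would also help to note that power is 89% if all 75 + 25 subjects are evaluable.

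For consistency, name Fisher's exact test for recurrence in section 8.2, so that sections 7.3, 8.1 and 8.2 agree.

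The cost is a short edit in section 8.1 and a test name in section 8.2. The stated power becomes about 3 points less favourable. Enrolment and the analysis method stay as they are.
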